9.5.3 Vital Signs and Weight

Systolic and diastolic blood pressure (mmHg), radial pulse (beats/minute), respiratory rate (breaths/minute), weight (kg), and temperature (°C) will be obtained at baseline and each study visit and recorded on the eCRF.

All vital signs and weight measurements as well as change from Baseline for these measurements will be summarized at each visit. A listing of weight and vital signs will also be provided.

The number and percentage of subjects with potentially clinically significant vital signs will be summarized at each visit. A listing of subjects with potentially clinically significant vital signs will also be presented. Table contains the criteria for identifying potentially clinically significant vital sign vital sign values.

Vital Sign Parameter	Criteria
Systolic Blood Pressure (mmHg)	>160 mmHg or increase of ≥20 mmHg from baseline
Systolic Blood Pressure (mmHg)	<95 mmHg or decrease of ≥20 mmHg from baseline
Diastolic Blood Pressure (mmHg)	>110 mmHg or increase of ≥15 mmHg from baseline
Diastolic Blood Pressure (mmHg)	<50 mmHg or decrease of ≥15 mmHg from baseline
Heart Rate (bpm*)	>100 bpm or increase of \geq 15 bpm from baseline
Heart Rate (bpm*)	<50 bpm or decrease of ≥15 bpm from baseline
Weight (kg) Gain	>10% weight increase
Weight (kg) Loss	>10% weight decrease

 Table 2:
 Criteria for Identifying Potentially Clinically Significant Vital Sign Values

*bpm = Beats per minute

9.5.4 Physical Examinations

The Investigator or designee will perform a complete physical examination at screening and at the final visit. The number and percentage of normal and abnormal physical exams will be summarized by body system at screening and at the final visit. Any clinically significant physical examination findings will be reported and analyzed as AEs or SAEs. Physical examination findings will also be listed.

9.6 Secondary Endpoints

9.6.1 Visual Analogue Scale of Pain Intensity (VASPI)

The VASPI will be a single question assessing how severe a subject's pain is 'right now'.

Scoring is based on the continuous visual analog scale (measured in mm) ranging from no pain at the start of the scale to unbearable pain at the end of the scale. VASPI will be assessed at Baseline and each study visit, including the final visit. The VASPI scores, as well as change from baseline, will be summarized at each visit. All assessments will be listed.

9.6.2 Brief Pain Inventory (BPI)

The BPI will consist of two domains, pain severity and pain interference with functioning.

Pain severity will be evaluated by rating pain on a scale from 0 (no pain) to 10 (pain as bad as you can imagine) for the 'worst', 'least', and 'average' pain experienced in the past 24 hours, as well as, the pain experienced 'now'. In addition, a calculated mean pain severity score will be based on the sum of all 4 of the pain scores divided by 4. If any of the 4 questions are missing, then the calculated mean pain severity score will be considered missing.

Pain interference with daily functioning will be evaluated by rating interference on a scale from 0 (does not interfere) to 10 (completely interferes) for 'general activity', 'mood', 'walking ability', 'normal work', 'relation with other people', 'sleep', and 'enjoyment of life'. A calculated mean pain interference will be based on the sum of non-missing interference questions answered divided by the number of questions answered. The mean should be set to missing if fewer than 4 pain interference questions are answered.

The BPI will be assessed at Baseline, Day 28, Day 80, Day 160, Day 286, and at the final visit. The BPI scores, as well as change from baseline, will be summarized at each specified visit for the following: pain severity 'worst', pain severity 'average', calculated mean pain severity, and calculated mean pain interference with function. All assessment, including the calculated mean scores, will be listed.

9.6.3 Patient Global Impression of Change (PGIC)

The PGIC will be a single question that rates the overall change, if any, from Baseline in activity limitations, symptoms, emotions, and overall quality of life related to the subject's painful condition based on a 7-point Likert scale from 1 (no change) to 7 (a great deal better).

The PGIC will be assessed at Baseline, Day 28, Day 80, Day 160, Day 286, and at the final visit. The PGIC score will be summarized at each specified visit. All assessment will be listed.

9.7 Clinical Opiate Withdrawal Scale (COWS)

The Clinical Opiate Withdrawal Scale (COWS) assessment will assess the severity of 11 opiate withdraw symptoms. Each symptom severity score ranges from 0 (asymptomatic) to a maximum of 3, 4, or 5 (severe based on criteria for the individual symptom). A total score is calculated based on the sum of the individual symptoms scores. The assessment will be performed at Baseline and the final visit to evaluate any opiate withdrawal symptoms. The COWs total scores

will be summarized at each visit and the changes from baseline to the final visit will also be summarized. Individual item scores and the total score for the COWS will also be listed.

10 Summary of Amendments to the SAP

After the initial SAP approval (version 1.0), all major or minor amendments will be summarized in the table below.

Version	Change (Reason)
2.0	Changed sponsor information (MNK acquired CNS Therapeutics).
	• Text for study objectives, endpoints, study design, and schedule of events all updated to match protocol amendment 4.0 dated 16Sep2014 which 1] clarified aspects of the study design that were unclear due to the complicated nature of the study, particularly with regard to conversion from morphine to study drug and 2] better organized the flow of text throughout, including language with regard to endpoints – see protocol amendment change summary for individual details).
	 Added clarification that submission objectives would be met when 300 subjects had 6 months of exposure and 150 subjects had 12 months of exposure (reflect protocol amendment 4.0 dated 16Sep2014).
	 Rewrote text regarding analyses of AEs (improve section flow and better describe the analyses themselves).
	• Updated text for evaluation of granulomas to match protocol amendment 4.0 dated 16Sep2014 and clarified that analyses would be performed for both possible and confirmed granulomas, as well as, added text describing the evaluation of granuloma signs and symptoms (reflect protocol amendment 4.0 dated 16Sep2014).
	 Include definitions for clinically significant vital sign changes for systolic/diastolic blood pressure and weight (added for clarification).
3.0	Typos corrected (clean up of document)
	 Clarified timing of main objective is at 12-months exposure for the 2mg/mL and 10mg/mL concentrations (based on protocol amendment 5 dated 18Dec2014).
	• Updated medical history text to describe the coding of terms (clarification).
	 Removed text that indicated latest version of MedDRA would be used for AE coding (dictionary version should remain stable to avoid constant recoding through long duration of study.
	Changed protocol deviation to protocol violation (to match MNK standards).

	 Consolidated and moved description of BPI, PGIC, and VASPI into a secondary endpoints section (improve flow). Updated analyses of BPI (analysis was updated to conventional published description whereby the BPI is assessed based on 2 domains separately: pain severity and interference with daily function). Added some description details to the PGIC, VASPI, and COWs (provided basic details on how the assessments were structured but made no changes to the original analyses).
4.0	 Added Summary of Amendments to the SAP section (provide historical reference). Described the timeline of sefety and officaely analyses for the study.
7.0	 Described the timeline of safety and emcacy analyses for the study Described the exclusion of subjects from Site 028 Clarified the analysis populations Added Appendix A – list of Tables and Listings for output Added Appendix B - documentation of Site 028 closure Corrected version dates of protocol and amendments

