3.0 STUDY DESIGN

3.1 Description of Trial Design

This is an open-label, single-arm study to evaluate the safety of hydromorphone hydrochloride given by continuous intrathecal infusion using an implantable pump device. This clinical trial will be conducted at up to 30 clinical trial sites that are experienced with the use of intrathecal opioids. This study will enroll both subjects on a current opioid (eg, morphine or hydromorphone hydrochloride) intrathecal medication as well as naïve subjects not currently on intrathecal opioid medications. Dosing regimens allowed in this study will include simple continuous, complex continuous and Personal Therapy Manager (PTM) dosing.

For subjects entering the trial already on a therapeutic dose of another intrathecal hydromorphone hydrochloride, the hydromorphone hydrochloride will be replaced by the study

drug (hydromorphone hydrochloride for intrathecal injection) on a 1:1 basis without dose adjustment or optional titration days. The subject is considered at a therapeutic dose and will start the study on Day 1.

Subjects converted from an intrathecal opioid therapy other than hydromorphone hydrochloride to the study drug will be dosed with the study drug according to the following conversion scheme:

Subject on Morphine or on another Opioid ³	Conversion Ratio
Dose ≤ 30 mg IT morphine and tolerating therapy well	1:61
Dose > 30 mg IT morphine or subject has significant side effects on morphine	1:12 ²

¹Conversion is based on mg-morphine equivalence such that for each 6 mg morphine sulfate the dose is converted to 1 mg hydromorphone hydrochloride.

Subjects who are converted directly to the study drug based on the 1:6 morphine-equivalence ratio are, by definition, at a therapeutic dose and must start the study on Day 1 without titration. Dose adjustments may be performed at subsequent visits, based on the investigator discretion.

For subjects using 1:12 conversion ratio, due to safety considerations, the conversion will be followed by up to five (5) optional titration days (Titration Days A, B, C, D and E) to achieve a therapeutic dose that is well tolerated before starting Day 1. These optional titration days may be three (3) to fourteen (14) days apart.

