9.5 Final Visit

Subjects will return to the investigational site for the final visit at approximately Day 365 (12 months after long term treatment starts) or when discontinued from the study for any reason. At the final study visit subjects will be assessed for AEs and clinical signs or symptoms of a granuloma as well as other procedures according to Appendix A. At the final study visit, the investigator will remove the residual study drug from the subject's pump and will replace the study drug with standard of care medication/therapy.

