Appendix A: Schedule of Study Procedures									

Table A-1: Schedule of Study Procedures

Study Procedure					Visit Schedule								
Study Day ^a	Screening Days -14 to 1 ^b	Baseline Days -3 to 1 ^b	Baseline for HYD201US Subjects ^b	Optional Titration Days ^{b,c}	Day 1 ^{b,d}	Day 28	Day 56	Day 80	Day 104	Day 160	Day 216	Day 286	Final Study Visit Day 365
Signed Informed Consent	X ^e		X										
Medical History ^f	X		*										
Complete physical exam ^g	X		*										X
Vital signs and Weight ^g	X	X	*	X	X	X	X	X	X	X	X	X	X
Urine pregnancy test ^g	X	X	X										X
ECG ^g	X		X										
CBC, CMP, Urinalysis ^g	X		X										
Concomitant medication assessment	X	X	*	X	X	X	X	X	X	X	X	X	X
Adverse event assessment	X	X	*	X	X	X	X	X	X	X	X	X	X
Hydromorphone Hydrochloride Pump Dose Adjustment and Refills h,I,l			X	X	X	X	X	X	X	X	X	X	X^{l}
Oral Opioid			X										·
Clinical evaluation for Granulomas ^j	X		*		X	X	X	X	X	X	X	X	X
VASPI Assessment ^k	X	X	*	X	X	X	X	X	X	X	X	X	X
COWS Assessment ^k		X	*	X									X
BPI^k		X	*			X		X		X		X	X
PGIC ^k		X	*			X		X		X		X	X

- a. Study Day is based on Day 1 defined as the first day a subject achieves a therapeutic dose of hydromorphone therapy. There is no Day 0 in this trial. Optional titration days for subjects below therapeutic levels will not be counted towards the 365 day study period. All visit days are +/- 7 days during the long-term extension phase of the study. Additional unscheduled visits may be scheduled to make dose adjustments or prescribe oral medication to manage pain and withdrawal symptoms as deemed appropriate by the investigator.
- b. Screening period is 14 days. Screening, Baseline and/or Initiation of Dosing (ie, Optional Titration Day or Day 1) visits may be combined. For subjects entering the CNS-HYD202US clinical trial that are transitioning from the CNS-HYD201US efficacy trial, these subjects will not be required to repeat Screening. For these subjects the last day of the CNS-HYD201US trial will be considered the first day (either optional titration day or Day 1) of the CNS-HYD202US trial. Baseline assessments will be completed as part of the final day (Day 119 or Treatment Failure day) and only additional activities or tests shown on the Schedule of Events (shown in table of events as "X") for these subjects are required to enter the CNS-HYD202US trial. Tests that are done as part of the final visit of the CNS-HYD201US trial and will not be repeated in this study are shown in the table with a "*".

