ECG ^g	X		X										
CBC, CMP, Urinalysis ^g	Х		Х										
Concomitant medication assessment	Х	Х	*	Х	Х	Х	Х	Х	Х	Х	Х	Х	Х
Adverse event assessment	X	Х	*	Х	Х	Х	Х	Х	Х	Х	Х	Х	Х
Hydromorphone Hydrochloride Pump Dose Adjustment and Refills ^{h,I,I}			X	X	X	X	Х	X	Х	Х	X	X	X ^l
Oral Opioid			X										- >
Clinical evaluation for Granulomas ^j	Х		*		Х	X	Х	Х	Х	Х	Х	Х	Х
VASPI Assessment ^k	X	Х	*	Х	Х	X	Х	Х	Х	Х	Х	Х	Х
COWS Assessment ^k		X	*	Х									X
BPI ^k		X	*			X		Х		Х		Х	X
PGIC ^k		Х	*			X		Х		Х		Х	X

a. Study Day is based on Day 1 defined as the first day a subject achieves a therapeutic dose of hydromorphone therapy. There is no Day 0 in this trial. Optional titration days for subjects below therapeutic levels will not be counted towards the 365 day study period. All visit days are +/- 7 days during the long-term extension phase of the study. Additional unscheduled visits may be scheduled to make dose adjustments or prescribe oral medication to manage pain and withdrawal symptoms as deemed appropriate by the investigator.

b. Screening period is 14 days. Screening, Baseline and/or Initiation of Dosing (i.e. Optional Titration Day or Day 1) visits may be combined. For subjects entering the CNS-HYD202US clinical trial that are transitioning from the CNS-HYD201US efficacy trial, these subjects will not be required to repeat Screening. For these subjects the last day of the CNS-HYD201US trial will be considered the first day (either optional titration day or Day 1) of the CNS-HYD202US trial. Baseline assessments will be completed as part of the final day (Day 119 or Treatment Failure day) and only additional activities or tests shown on the Schedule of Events (shown in table of events as "X") for these subjects are required to enter the CNS-HYD202US trial. Tests that are done as part of the final visit of the CNS-HYD201US trial and will not be repeated in this study are shown in the table with a "*".

c. Optional titration days are intended for subjects requiring titration after switching from other opioids or control arm subjects enrolling after completion of the CNS-HYD201US trial. Titration days are only if needed to achieve a therapeutic dose of hydromorphone after which subjects will start on Day 1 of the trial. Optional titration days may be scheduled from 3 to 14 days apart depending on the investigator discretion.

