d. Day 1 of the trial is considered the first day of the long term extension period. All subjects should be titrated to a therapeutic dose prior to starting Day 1. Day 1 may include a dose adjustment as needed.

e. Informed consent for subjects entering the CSN-HYD202US trial after completion of the CNS-HYD201US trial may be obtained as early as 30 days prior to completion of the CNS-HYD201US trial.

f. For subjects entering the CNS-HYD202US trial from the CNS-HYD201US trial, medical history will be carried over from the previous trial and does not need to be repeated.

- g. For subjects entering the CNS-HYD202US trial from the CNS-HYD201US trial, Physical Examination, will be completed on the final visit day of the CNS-HYD201US trial, which is Day -1 of the CNS-HYD202US trial.
- h. Pump refills will be conducted as necessary to adjust the treatment regimen and conduct pump refills. Pump refills are not required at all visits.
- i. Dose adjustments are allowed during the long-term follow up period both as an increase or decrease to optimize the dose. The maximum dose is 10 mg/day of hydromorphone hydrochloride.
- j. If there are clinical signs of a granuloma as defined in in the protocol, the Medical Monitor should be notified and an MRI (with and without contrast) or CT myelogram scheduled to confirm the pathology of the granuloma.
- k. VASPI, COWS, BPI and PGIC are administered at the study site on specified visits.
- 1. At the final study visit, the investigator will remove the residual study drug from the subjects pump and will replace the study drug with normal standard of care medication/therapy.

5 Data Management

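### SAP 9.7 omits the scheduled titration-day COWS readings, and its only change score, Baseline to final visit, cannot show transient withdrawal during conversion or titration

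*SAP*

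**What the plan says.** **Timing in the SAP text.** SAP 9.7: "The assessment will be performed at Baseline and the final visit to evaluate any opiate withdrawal symptoms". Titration days are not mentioned.

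**Timing in the schedules.** The "COWS Assessment" row of SAP Table 1, and the same row of Protocol Table A-1 (Appendix A), mark Baseline, Optional Titration Days and the final visit. For subjects coming from CNS-HYD201US, the baseline reading is taken from that trial's last visit. The footnote to the SAP table adds that "VASPI, COWS, BPI and PGIC are administered at the study site on specified visits".

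**Analysis.** SAP 9.7 says the total scores "will be summarized at each visit and the changes from baseline to the final visit will also be summarized", and that "Individual item scores and the total score for the COWS will also be listed". SAP Appendix A carries this as Table 14.3.5.8 (ITT Population) and Listing 16.2.13 (all enrolled subjects).

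**Who titrates.** For subjects converted at 1:12, Protocol 3.1 says "the conversion will be followed by up to five (5) optional titration days", spaced 3 to 14 days apart. Intrathecal-naive subjects may also have up to five, and CNS-HYD201US control-arm subjects who had been titrated off have one or more. Under Protocol 3.1, subjects entering at 1:1 or 1:6 start on Day 1 without titration.

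**Final visit.** Protocol 9.5: "At the final study visit, the investigator will remove the residual study drug". No COWS is scheduled after that visit.

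**The concern.** The SAP's text contradicts its own schedule about when the scale is given. The readings left out are the only scheduled ones that can fall soon after a subject starts or converts to study drug. A programmer working from 9.7 alone could build the COWS table from two visits, roughly a year apart for a completer.

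The change score has a separate limit that does not depend on how the contradiction is resolved. A difference between the first and last readings carries no information about a rise and fall between them. The report could therefore show withdrawal scores for this open-label safety trial without any summary of how many subjects had raised scores while being converted or titrated.

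**Working it through.** No figure is stated for COWS, and the trial plans no formal testing, so the check is a comparison of the texts.

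**Step 1: visits side by side.**

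| Visit | Protocol Table A-1 | SAP Table 1 | SAP 9.7 text |
|---|---|---|---|
| Baseline (or CNS-HYD201US last visit) | yes | yes | yes |
| Optional Titration Days (up to five) | yes | yes | not mentioned |
| Day 1, 28, 56, 80, 104, 160, 216, 286 | no | no | no |
| Final visit | yes | yes | yes |

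The two schedules agree with each other. Only the 9.7 text differs.

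**Step 2: how many readings are affected.** A subject who titrates has at most 1 (Baseline) + 5 (titration) + 1 (final) = 7 scheduled readings, and 9.7 names 2, leaving up to 7 − 2 = 5 unnamed. This is a maximum: titration days are used only as needed, and the schedule allows the first to be combined with the Baseline or initiation visit. A subject entering at 1:1 or 1:6 has 2 scheduled readings, and 9.7 names both.

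**Step 3: the two readings of the by-visit summary.**

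- If visits means those named in the preceding sentence, titration-day totals enter no table and appear only in Listing 16.2.13.
- If visits means those in SAP Table 1, titration-day totals are summarised in Table 14.3.5.8.

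The neighbouring sections favour the first reading. SAP 9.6.2 (BPI) and 9.6.3 (PGIC) each list their visits in full, and those lists match Table 1 exactly. SAP 9.6.1 (VASPI) says Baseline and every study visit. If 9.7's list is equally complete, titration days are outside it. This is an inference; the text does not settle it.

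**Step 4: what the change score can show.** Write B for the Baseline total, T₁ to Tₖ for the titration-day totals (k at most 5) and F for the final total. The planned change is F − B, which contains no T. Two subjects with the same B and F get the same change whatever happened in titration. Per-subject changes Tⱼ − B and the maximum of the Tⱼ do carry that information, and 9.7 plans neither.

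**Step 5: even the generous reading leaves a gap.** Titration days are optional, so each later one includes only subjects who still needed titration. Visit-by-visit means are then taken over changing sets of subjects and do not count how many ever reached a given level. The form in Protocol Appendix D already bands totals (5–12 mild, 13–24 moderate, 25–36 moderately severe, above 36 severe), but 9.7 does not use the bands.

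**The case against.** The strongest reply is that little is lost.

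- **The change score is not the whole analysis.** A reader might infer that the plan analyses only Baseline-to-final change. It does not: 9.7 also summarises totals by visit and lists every item and total score. This stands. What remains is the uncertainty over which visits are meant and the absence of a titration-day change or peak.
- **COWS is not the only source.** A reader might take it for the trial's sole measure of withdrawal. Protocol 5.1 collects adverse events during titration days, the schedules mark that assessment there, and SAP 9.5.1 tabulates events beginning or worsening after first study drug. This largely stands. The cover is less tidy than it looks, because Protocol 13.1 dates the reporting period from first administration on Day 1, while the schedule places Day 1 after titration.
- **The final visit can be informative.** A reader might infer that it cannot show withdrawal, or that the change must be near zero. No expected COWS values are given. Protocol 9.5 and 11.0 apply final-visit procedures to subjects who stop early, and Protocol 3.8 and 10.0 have non-compliant or discontinued subjects weaned or titrated off. Control-arm subjects from CNS-HYD201US had been titrated off before entry, so their Baseline may itself be raised. This stands, and it rules out labelling the Baseline-to-final change as not a measure of withdrawal.
- **Titration as the period of greatest risk.** This is plausible clinically, but no section says so. Titration also serves naive subjects starting low, and Protocol 9.3 permits oral opioids during it.
- **The conversion ratios as a measure of size.** The difference between 1:6 and 1:12 describes dosing and quantifies no effect on COWS.
- **COWS is a minor measure.** It is outside the primary and secondary endpoints. This stands and limits the weight of the point.

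**Conclusion.** The point holds in a narrow form. SAP 9.7 contradicts SAP Table 1 and Protocol Table A-1 by leaving out titration days, does not make clear whether its by-visit summary covers them, and defines no change or peak score for them on either reading. The planned Baseline-to-final change cannot show transient withdrawal during conversion or titration.

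The size is up to five unnamed readings per titrating subject and none for subjects entering at 1:1 or 1:6. The documents do not say how many subjects titrate and give no COWS values, so no bias or missed-event count can be calculated. The trial's conclusions do not turn on this; it is a worthwhile small improvement to a descriptive safety table.

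Two assumptions apply. The first is that titration-day COWS was recorded as scheduled. The second is that the recorded data are usable: SAP 8.4 says safety modules were cleaned and the VASPI, BPI and PGIC modules were not cleaned after 11 September 2017, but it does not say which group COWS belonged to.

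**What to change.** 1. In SAP 9.7, give the assessment times as Baseline, Optional Titration Days and the final visit, matching Table 1, and state that the by-visit summary includes titration days.
2. In Table 14.3.5.8, add change from Baseline at each titration day, with the number of subjects assessed.
3. In the same table, add each titrating subject's highest titration-day total after first study drug, by the Appendix D bands. Include a row for totals under 5, which the form leaves unnamed. Exclude any reading taken before first study drug at a combined visit. Give the number of readings per subject, since more readings give more chance of a high one.
4. Where numbers allow, split item 3 by entry route: 1:12 converters, subjects naive to or weaned off intrathecal therapy, and CNS-HYD201US control-arm subjects.
5. Report final-visit COWS and its change from Baseline separately for completers and early discontinuers.
6. State whether the COWS module was cleaned before lock.

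The assessments are already scheduled and the database is locked, so the cost is a text correction and some table programming. No new data are needed. The change does not inform on subjects converted 1:1 or 1:6, for whom Baseline and the final visit remain the only scheduled readings.
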